Children and young people (CYP) have unmet health and social needs, especially those with neurodevelopmental impairment. These could be addressed through social prescribing (SP). SP is a key component of universal personalised care, supported in the NHS Long Term Plan. It involves link workers (LW) helping those with health and social care needs to engage with supportive community resources. Its current focus is on adults.

Aim:

To identify the components of effective SP for CYP, identifying lessons learned across two settings.

The two settings are:

- 1) Great North Children's Hospital (GNCH - new hospital pilot study)
- 2) Zone West (ZW - ongoing community study)

This protocol describes the arrangements for the GNCH pilot study, additional elements of fieldwork for an ongoing ZW study and the joint evaluation of social prescribing across the GNCH hospital setting and the community Zone West setting.

Study Design	Mixed-methods evaluation
Study Participants & Planned Sample Size	
▪ Link Workers (n=4)▪ Children and young people and their carers (n=60, 30 from each setting).
Follow-up Duration	Up to 6 months
Planned Study Period	
▪ Start date: 31/03/2022▪ Duration: 20 months

Funding and Support in Kind

Financial support for the project is being provided by:

- Great North Children's Hospital Foundation
- Ways to Wellness
- NIHR ARC NENC

Study Flowchart

For the Zone West project, only the interviews and observations are in addition to current practice. The GNCH pilot is entirely new.

1. Background and Rationale

Many children growing up in the North of England face challenges due to deprivation¹. Deprivation adversely affects long-term outcomes². The COVID-19 pandemic heightened these pre-existing problems and added new ones of social isolation, mental health and disrupted service provision, leading to high levels of unmet need^{3,4}. Against this backdrop, children with chronic complex healthcare problems (of which neurodisability forms the largest group) have particularly high levels of unmet non-medical needs. More than half of families with a child with complex healthcare needs have financial difficulties, and a third express difficulty accessing non-medical services⁵. More support for these children and their families is urgently needed.

Social prescribing (SP) is a development currently being established in primary care networks, in which 'link workers' support those with health and social needs to find and engage with community resources to help their health and wellbeing⁶. SP is a key component of universal personalised care, supported through NHS England as part of the NHS Long Term Plan. There is emerging evidence from SP schemes in adults (including Ways to Wellness), of benefits to wellbeing and in some cases reductions in NHS costs [see <https://www.kingsfund.org.uk/publications/social-prescribing>]. SP schemes for CYP are emerging, e.g. Streetgames (who also oversee a CYP SP network). However, a recent systematic review found *no* published studies of SP for CYP⁷. Since then, Bertotti et al.⁸ reported a 2-year evaluation of SP for young people (YP), demonstrating improved mental wellbeing, reduced use of NHS and social care, and evidence of a social return on investment well above the average for adult SP schemes. They recommend further "test and learn" approaches to SP for YP, and research into the specific skills required for LW supporting this group.

Our proposal addresses these recommendations whilst complementing the studies in Bertotti's report. The average age of participants in Bertotti's report was 16 years, whereas we investigate a younger group. We will evaluate the established community-based Zone West programme for primary school aged children. Furthermore, we will set up and evaluate an innovative scheme to support children with neurodisability and their families – an approach endorsed by respondents to our preparatory surveys and extensive stakeholder discussions. Both schemes will undertake outcomes evaluation separately as part of their internal working. This project addresses a mixed-methods evaluation of SP for CYP across settings, identifying components for best practice.

Some general principles of SP are clear. Schemes require understanding of and engagement with local community assets⁹. Participant engagement is enhanced by: good explanation of the scheme and potential benefits at referral; accessibility and quality of the resource; and a supportive LW¹⁰. Our project explores the challenges of SP for a younger, less independent group of children including those with disability, for whom acknowledging the support role but also the needs of the family, is key.

2. Theoretical Framework

The social determinants of health have long been known – for example, the relationship between serious adverse life events and depression¹¹; and between poverty and life expectancy as described in the Marmot Review and follow-on report¹². The effect is evident right from early childhood: for example, children and young people from deprived backgrounds are more likely than average to attend Accident and Emergency departments, and to be admitted to hospital¹³. There is a strong association between developmental disabilities and socio-economic disadvantage¹⁴. All these examples highlight the negative effects of deprivation and adverse events on health; conversely, positive social influences can mitigate against these effects.

Social capital describes “the extent and nature of our connections with others and the collective attitudes and behaviours between people that support a well-functioning, close-knit society”¹⁵. Social capital is important for well-being at the level of the individual and the wider community. Achieving health and well-being at the level of the individual clearly requires inputs tailored to the individual’s needs and preferences – this underpins the principles of personalised care. Social prescribing is a key component of universal personalised care and is supported in the community through NHS England as part of the NHS Long Term Plan¹⁶.

The salutogenic model of health¹⁷ provides a potentially useful framework within which to consider what might be key components of good link worker practice. This model views health as a continuum rather than as a dichotomous state in relation to disease; and focusses on promoting factors which may support the individual in achieving improved health wherever they are on the continuum. The model incorporates the view that an individual’s “sense of coherence” (essentially a reflection of personal resilience) influences their health¹⁸. Unfortunately, this presents a limitation for the current study in that sense of coherence may not be measurable in a number of participants.

Husk et al.¹⁰ undertook a realist review which aimed to clarify what processes are involved in effective social prescribing interventions for adults in a community setting. They identified three key stages – enrolment, engagement and adherence. Enrolment by the participant is underpinned by a belief that the social prescribing process will be beneficial, and by the referral being presented in an acceptable way. Engagement in prescribed activities is more likely if these are accessible to the participant and if transit to the first session is supported. Adherence with the program is more likely if the activity leader is skilled; adherence may also be affected by a change in the participant’s medical condition.

Tierney et al.¹⁹ also undertook a realist review, focussing on the role of the link worker in primary care and using a “context-mechanism-outcome” approach to provide a testable programme theory to explain how social prescribing works and in what conditions. Two key concepts arose – “buy-in” to the service, and establishing and maintaining good relationships between the link worker and other stakeholders including healthcare professionals, patients and the voluntary sector. Buy-in required support from key stakeholders; clear information about the nature of the service; and confidence in the capability of the individuals employed as link workers. Potential outcomes included improved wellbeing and reduced use of GP services. They then drew upon the existing theories around social capital and “Patient activation” (which relates to the “sense of coherence” mentioned above). Their theoretical framework is an appropriate starting point for our study but is likely to require modification in light of the participant group under study. The additional factors of relevance in our study are the age group (children), and for the hospital pilot (in addition to this setting), the presence of neurodisability. These factors raise additional challenges related to the relative lack of

independence/autonomy of the group under study; physical challenges such as restricted mobility; communication challenges related to the age and/or underlying condition of the young person; and negotiating the hospital setting which in the first instance will likely be unfamiliar to the link worker.

3. Research Question/Aims

To identify the components of effective social prescribing (SP) for children and young people (CYP) and their families, identifying lessons learned across two settings.

3.1 Objectives

- 1. Describe, understand and explain social prescribing for CYP across the two settings** We evaluate SP for CYP across two settings – one existing service, Zone West (ZW) and one newly established, Great North Children's Hospital (GNCH) - to identify effective components of practice to guide recommendations for training and service delivery.
- 2. Identify, understand and explain effective link worker behaviours, and barriers and facilitators to service engagement** This analysis will inform development of a more broadly applicable model for SP service provision for CYP and their families.
- 3. Identify, understand and explain how regional and national policy can support and improve SP for CYP and their families.**
We will ensure lessons learned are applied as widely as possible. We have a large and experienced steering group including representation from local CCGs, Newcastle City Council SEND board, NECS and NHS Improvement who will advise on how the policy environment is shaping support for CYP, and how to support wider adoption of the approach.

3.2 Outcome

We intend that our study will lead to a greater understanding of how to provide optimal social prescribing services supporting children and young people and their families, across different settings and circumstances. This will include a description of effective link worker behaviours as well as broader aspects of service provision. We intend to disseminate these findings. Our intention is that the findings would be used to optimise service provision including components such as link worker training, and to inform regional and national policy on SP for CYP.

4. Study Design and Setting

4.1 Study Design

A mixed-methods evaluation.

4.2 Participants & Setting

Link workers (n=4) and children and young people and their families/carers (n=60; 30 per site) will be recruited. This is a multicentre study.

Hospital-based site: This new pilot service will situate the identification, referral and initial assessment in a hospital setting and will target those with high levels of unmet need who are embedded in secondary/tertiary care.

Community-based site: Newcastle's ZW project is an existing service, supporting children aged 7-11 years with concerns raised from education, health and/or social care (see <https://www.northeastwellbeing.co.uk/zone-west/>). Research governance approvals are in place for the existing service and evaluation (IRAS ID 266176) – this application simply includes the addition of qualitative observations and interviews of participants and their families in that study.

4.3 Intervention

Link Workers (LW) at the Community site and the Hospital site will establish peoples' individual profiles of need, identify and support clients to engage with relevant services, reviewing progress at 3 and 6 months.

In practice, this will mean (both sites):

- Person identified as potentially eligible
- Consent for referral to LW (through standardised pathway) and study participation
- LW meets participant, builds relationship, records demographic data; documents profile of need (guided by parents as proxy where necessary). For the hospital-based project, related needs of close family members will be similarly captured.
- LW identifies and discusses relevant resources with participant.
- Participant accesses resources, with support if needed.
- LW follows up with tailored support (e.g. contact every 2-4 weeks as necessary) and reviews at 3 and 6m

The TIDIER²⁰ checklist below summarises the key features of the intervention in each setting.

Name	GNCH pilot	Zone West
Why	Children with neurodisability and their families have high levels of unmet need. SP is a plausible solution to addressing this.	ZW identifies primary school age children with needs in the dimensions of education, health and/or social care and assigns a LW to help address needs.
What Materials	Support star (Triangle) will be used by LW to gather information about domains and levels of need, at baseline and follow up. This will form the basis of a conversation about unmet needs in a range of domains. LW will receive training in its use.	A bespoke questionnaire forms the basis of a conversation about unmet needs in a range of domains.
What Procedures	Unmet needs will be mapped, and participants referred to (and supported to attend if need be) community services to address this need	Unmet needs will be mapped, and participants referred to (and supported to attend if need be) community services to address this need
Who Provided	Link workers – with relevant life experience, personal qualities and values to be able to undertake the work. Training includes: Social Prescribing - elearning for healthcare (e-lfh.org.uk) Plus some shadowing with link workers/hospital team. Optional training to fill in gaps in experience: Level 2/3 Information, Advice and Guidance; Level 2 Counselling; Life Coaching; Active Inclusion (welfare benefits); Motivational Interviewing; City of sanctuary (refugee and asylum)	Link workers – with relevant life experience, personal qualities and values to be able to undertake the work. Training: ZW LWs receive induction and training from existing LWs, which includes a period of shadowing existing LWs in schools
How Provided	Individual, face to face session at baseline. Ongoing follow up by telephone/virtual means, with face to face reviews at 3 and 6 months.	1:1 and group work.
Where	Children identified during inpatient hospital stay, where baseline assessments will occur. Engagement with LW (up to 6m) and community services within the North of Tyne and	Community-based, West end of Newcastle (Children who are patients at one of three GP practices and attend one of four primary schools)

	Gateshead ICP (indefinite) continues after discharge from hospital.	
When & How Much	The amount of intervention will be tailored to need, but LW intervention will be time limited to 6 months for practical reasons. During this time LW will make contact with participants at least once a month – but more regular contact may be required where there are high levels of need.	The link worker will identify key areas of need individualized for the child. They will then design a programme to match them with the appropriate assets within the community. The frequency of visits from the link worker will be determined by the link worker and the child/family.
Tailoring	This is a personalised intervention, adapted to address unmet need	This is a personalised intervention, adapted to address unmet need
Modifications	If recruitment through inpatients is slow we will also recruit through outpatients.	If recruitment is slow we could expand the number of GP surgeries
How Well (Adherence)	We will document LW contacts and whether participants accessed community resources to which they were referred, and where relevant, how long for. In-depth interviews will also explore adherence	We will document LW contacts and whether participants accessed community resources to which they were referred, and where relevant, how long for. In-depth interviews will also explore adherence.

The schedule of events is in the Appendix and details the assessments specific to each setting. For Zone West, the only change to the current service is the addition of observations and qualitative interviews. More details about the assessments are given below in section 5.

5. Methods of Data Collection and Data Analysis

5.1 Data Collection

Three interrelated approaches will be used:

1. Qualitative data to understand features of optimal service

1a. In-depth interviews with families

In-depth interviews with families (parents, and children including siblings where appropriate/possible) will be undertaken. We will use purposive sampling to explore experiences of families/children (n=15 per site) with differing needs and backgrounds, to start to establish what works, for whom, when and how.

We will encourage them to bring photos of meaningful moments during community engagement sessions to aid in expression of what they found beneficial as well as what they found challenging (photo elicitation methods). [name], (Co-I) has experience of using photovoice methodology²¹⁻²³ and the approach is particularly valuable for eliciting the experiences of people with disability^{24,25}. In a photo elicitation study, cameras are given to individuals in order to capture photographic images around a central theme which is of concern. These photographs are then used to facilitate interview-style discussions to explore the theme further. The photographs and findings from the discussions are then shared with the wider community stakeholders, often in the form of a workshop²⁶. The reason for choosing photo elicitation as a method is that we are interested in understanding the potentially unanticipated perspectives of carers. Unlike more traditional methods of enquiry (e.g. research led structured interviews), the aim of photovoice is to centre the framing of a topic directly around the perspectives of the study participants and elicit what is important to them from a first-hand perspective²⁷.

Commencing after the baseline assessment, families will be trained in the photo elicitation method. They will be instructed to capture images related to their experiences. We will hold discussions at 3 and 6 months with the participants, where we will undertake an in-depth discussion with the photographs as prompts/starting points.

Discussions will be framed around the 'SHOWED' mnemonic; a commonly deployed method in photovoice studies²⁸, which consists of five questions;

1. What do you **S**ee here?
2. What is really **H**appening here?
3. How does this relate to **O**ur lives?
4. **W**hy does this condition **E**xist?
5. What can we **D**o about it?

Individual interviews with the participants will be conducted until data saturation.

1b. Qualitative Observation

Qualitative observation of interactions between link workers and children/families, and of engagement with services (n=15-30 per site), using audio recordings where consent is provided, to identify components of good practice.

1c. Short, informal debriefs

Short, informal debriefs with the LW every two weeks to understand service issues.

We anticipate a mixture of face to face and virtual (telephone or Teams) interviews, factoring in flexibility in relation to potential developments with the COVID-19 pandemic and also convenience and resources available to families. A topic guide, developed by the research team including parent advisors, will be used to guide the interviews but will not be restrictive.

2. Quantitative process data to understand pathways and throughput.

We will use routinely collected data on the number of referrals, uptake rate, continued engagement rate and numbers declining or deemed inappropriate for referral; demographics; number and nature of community groups referred to and engagement with these; time spent by LW per person and nature of work

3. Quantitative pre- and post-intervention data.

Baseline data collection including demographics and contact details for families will be collected in both settings, and forms part of standard care for link worker interventions.

Pre and post intervention data will be collected at each setting, covering the domains of:

- Profile of needs
- Quality of life and wellbeing
- Specific data relevant to the population under study.

Specifically, we will cover:

3a. GNCH site - Pre- and post-intervention data (i.e. at baseline, end of intervention and at 6m)

- The Support Star will be used by the link worker as part of the assessment of needs. This does not form part of usual NHS care but is the method by which a link worker will gather information to guide the intervention and to record progress.*** The Support Star was designed for young people facing serious illness, with both young person and parent/carer versions available)
- The following questionnaires will be administered by the research team and are not part of routine data collection by link workers, but are gathered for the purposes of this study***
 - Wellbeing (Outcomes Rating scales including age <5y with proxy scoring) – takes <1 min²⁹
 - Quality of life (EQ-5D for adults; CHU-9D for children including proxy version) – takes <5 min

- Warwick-Edinburgh Mental Wellbeing Scale (parents) – takes <5 min
- Three questions to gauge financial strain on the family³⁰ – takes <1 min
The three financial strain questions are:-
 - o How often they or their household puts off buying something they need
 - o How much difficulty they or their household had paying bills in the last 12 months
 - o At the end of each month over the past 12 months, did they or their household end up with more than enough money left over, some money left over, just enough to make ends meet, or not enough to make ends meet

3b. Zone West site – form part of the routine ZW care

See schedule of events in Appendix, where these are covered for completeness but they form part of the routine ZW care and are covered by existing research governance approvals.

Data collected as part of the Zone West project will be stored securely on existing secure server (online case management system “Penelope” covered by existing research governance approvals. The ZW team will provide the research team with necessary demographic information regarding participants to be observed and interviewed; and will provide anonymised summaries for process evaluation and pre-post evaluation data.

Data collected as part of the GNCH pilot will be manually entered via a web-based form into a secure Management Information System (MIS) hosted by Ways to Wellness, in line with their usual practice for social prescribing clients. The MIS is provided by the company Vital Service (vital-service.io) which uses a Linux-based operating system. All of the data is hosted and stays on UK based servers. To access the system, a unique login and password are required (login is over a 256-bit HTTPS connection). LW will use this MIS to record the baseline demographic data and Support Star assessments as well as other notes regarding their interaction with participants (e.g. services referred to; follow up contacts etc.). The research team will be given read only access to the records for clients in this study and also “edit” access to an assessment section in which they can upload completed questionnaires and notes related to the research. Each application on the server has its own separate location within the server’s file system, its own databases, and separate access credentials for files and each database. The access control functionality within WtoW MIS ensures only authorised users can see the data they need to see, and no more. A software firewall is part of the wider server infrastructure on the server. WtoW also restricts access following multiple failed login attempts and has 2FA authentication provided by SMS enabled. (This means that the user has a specific username and password and must also authenticate each login with a code sent via text). A secure password reset system is in place through Vital Service. There is daily backup of the service with 7-day retention which is encrypted.

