5.2 Data Analysis

Descriptive statistics will summarise quantitative data on rates of eligibility, consent, recruitment and retention; summary statistics will be included for assessment and outcome measures; the setting-specific outcomes will be summarised for each setting separately to further understand each pilot but are not the main focus of the current application.

Interviews and observations, following participant's consent, will be recorded verbatim, transcribed (by an approved external organisation e.g. UK Transcription) and anonymised for analysis. Observation and informal debriefs will involve the production of contemporaneous anonymised fieldnotes. Photos will be collected. All qualitative analyses will be conducted according to the standard procedures of rigorous qualitative analysis. We will use procedures from first-generation grounded theory (coding, constant comparison, memoing), from analytic induction (deviant case analysis) and constructionist grounded theory (mapping). We will undertake independent coding and cross checking and a proportion of data will be analysed collectively in data clinics (with core research team) and workshops with stakeholders where people share and exchange interpretations of key issues emerging from the data. Qualitative interview and observation data (both sites) will be stored on a secure server on Newcastle University's system, with password protected access to the research team.

6. Sample and Recruitment

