10.2 Appendix 2 – Schedule of Procedures

10.2.1 Appendix 2.1 - Schedule of Procedures (GNCH Project)

Procedures	Visits						
	Screening	Baseline visit (LW)	Assesses	Follow up contacts and engagement with services	3 month assessments	Follow up contacts and engagement with services	6 Month assessments
Informed consent	x						
Demographics- done by LW		x					
History-taking (guided by Support Star) – done by LW		x			x		x
Wellbeing assessment - Outcomes Rating scales (proxy for age <5y) Warwick-Edinburgh Mental Wellbeing scale (parents)			x				x
Quality of life assessment - EQ-5D for adults - CHU-9D for children including proxy			x				x
Financial strain Qs			x				x
LW Telephone				Every 2-4 weeks		Every 2-4 weeks	

with X calls for support/assessment progress				depending on need		depending on need	
Observations by RA of LW sessions (15 total)		x			x		x
Observations by RA of engagements with services (15 total)				x			
In-depth Interview (15 participants)							x

Observations by RA – in red as no additional burden to participant.

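### Two of the three GNCH financial strain questions look back 12 months but are compared over 6 months, so half of the follow-up window predates the intervention

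*Protocol*

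**What the plan says.** Protocol Section 5.1, item 3a, lists the GNCH questionnaires under "Pre- and post-intervention data (i.e. at baseline, end of intervention and at 6m". Three questions on financial strain are among them, with their content set out:

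- Bills: "How much difficulty they or their household had paying bills in the last 12 months".
- Money left at month end: "At the end of each month over the past 12 months, did they or their household end up with" one of four ordered answers, from more than enough to not enough.
- Postponed purchases: "How often they or their household puts off buying something they need". This item states no recall period.

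Appendix 2.1 has a row "Financial strain Qs" with one mark at the baseline assessment and one at 6 months, and none at 3 months. The TIDieR table in Section 4.3 says "LW intervention will be time limited to 6 months for practical reasons", and the study summary gives follow-up of up to 6 months. Nothing in the protocol changes the wording for the follow-up visit or mentions the overlap.

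For analysis, Section 5.2 says "summary statistics will be included for assessment and outcome measures". It adds that setting-specific outcomes are summarised by setting and are not the study's principal interest.

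**The concern.** A before/after comparison needs the second answer to describe time after the intervention began. With a 12-month window and a 6-month gap, it does so only in part. The months are merged inside a single answer, so no later analysis can separate those before baseline from those after it. This is fixed by the questionnaire and the visit schedule and cannot be repaired in a statistical analysis plan.

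The item is not incidental to the rationale. Section 1 cites financial difficulties in more than half of families of children with complex healthcare needs, and the optional link worker training in Section 4.3 includes welfare benefits. GNCH has no control group, so the before/after summary is the only quantitative reading of financial strain that these questions can give. What is at stake is whether a reader of that summary can take it as change over the intervention.

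**Working it through.** The protocol states no expected change, variability or power for these items, so there is no figure to reproduce. The check is window arithmetic.

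**Inputs from the protocol.** Recall window 12 months for two items (Section 5.1). Follow-up reading at 6 months (Appendix 2.1). Intervention and follow-up of at most 6 months (Section 4.3, study summary).

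**Step 1: overlap.** With baseline at month 0, the baseline window is months -12 to 0 and the 6-month window is months -6 to +6.

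- Share of the follow-up window before baseline = (12 - 6)/12 = 50%.
- Section 5.1 also names an end-of-intervention reading, which Appendix 2.1 does not show separately. If that fell at 3 months, the share would be (12 - 3)/12 = 75%.

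**Step 2: even recall (assumption).** The shared months cancel, leaving

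observed change = 0.5 × (mean strain over months 0 to 6 - mean strain over months -12 to -6).

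With stable strain before baseline, and the full change reached by month 6 set to 1:

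| Course of the change | Calculation | Visible share |
|---|---|---|
| Immediate and lasting | 6/12 | 0.50 |
| Linear build-up over 6 months | (1+2+3+4+5+6)/6 ÷ 12 = 3.5/12 | 0.29 |
| Starts after month 3 | 3/12 | 0.25 |

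**Step 3: recall that favours recent months (assumption).** If the weight given to a month halves every h months going back, the latest 6 of 12 months carry the share 1/(1 + 0.5^(6/h)). For an immediate lasting change:

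- h = 12: 1/1.707 = 0.59
- h = 6: 1/1.5 = 0.67
- h = 3: 1/1.25 = 0.80

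Under the same three weightings, the linear build-up shows at 0.36, 0.43 and 0.55, and the late start at 0.32, 0.39 and 0.53.

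**Step 4: strain that rose before baseline (assumption).** Let strain be 0 in months -12 to -6 and 1 in months -6 to 0, with even recall. The baseline answer is 0.5.

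- The rise resolves fully after baseline: follow-up answer (6×1 + 6×0)/12 = 0.5, observed change 0. Monthly strain truly fell by 1.
- Nothing changes after baseline: follow-up answer 1, observed change +0.5. The true change is 0.

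**Step 5: ordered categories.** The answers are categories, so a halved shift need not look halved. If an underlying score is rounded to the nearest category and falls by 0.5 instead of 1, a start at 2.6 still moves one category (3 to 2), while a start at 2.45 does not move (2 to 2).

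**Step 6: shorter windows.** With a window of 6 months or less at the 6-month visit, the share before baseline is 0%. An immediate lasting change then shows in full. The linear build-up shows at 3.5/6 = 0.58 with a 6-month window and (4+5+6)/18 = 0.83 with a 3-month window.

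**The case against.** The strongest reply concerns size and consequence. A reader might infer that any change in financial strain is at least halved. The documents do not support that. It needs even averaging over the year, stable strain before baseline and a score that behaves like an interval scale, and the protocol establishes none of these. Steps 3 to 5 show that dilution can be milder, or that the error need not be dilution at all. The third question has no 12-month window, so the point does not reach it. This part of the reply stands.

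A reader might also infer that the pilot would wrongly report that social prescribing fails to relieve financial strain. The protocol plans no such conclusion. The aim and objectives in Section 3 concern components of practice, link worker behaviour and policy; Section 5.2 plans descriptive summaries; and Section 6.2.1 describes a pragmatic sample. No test or decision rests on these items, and about 30 uncontrolled families could not settle the question even with well-matched wording. Section 7.1 expects financial pressures to come up in discussion, and interviews take place at 6 months, so relevant experience may surface there. This limits the harm, but a descriptive summary of mismatched windows can still mislead.

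Finally, the 12-month wording has merits. It comes from a cited source, and a full year evens out seasonal bills. Both are real costs of changing it.

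**Conclusion.** The mismatch is real. For two of the three GNCH financial strain items, half of the follow-up window lies before the intervention and is counted in both answers. This follows from the protocol's own wording and schedule, without further assumption.

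The effect on the reported change does depend on assumptions. With even recall and stable prior strain, about half or less of the change is visible (25 to 50% in the cases worked). With recall weighted to recent months, an immediate change shows at 59 to 80%. If strain rose before admission, a true fall can vanish and a rise can appear where there was none. Dilution is the likely direction, but its size cannot be fixed from the documents.

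This should be fixed but does not threaten the study: it concerns two short items at one site, in a secondary descriptive strand.

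**What to change.** At both baseline and 6 months, ask the bills and month-end questions with one common reference period no longer than the time since baseline, for example the last 3 or the last 6 months. The 12-month wording may stay as an optional extra descriptor at baseline. A 3-month period picks up more of a gradual change than a 6-month one and leaves room if a visit falls early. If a separate end-of-intervention reading is intended, Section 5.1 and Appendix 2.1 should be brought into line and the period should fit that reading too.

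The cost is a change to the questionnaire and an amendment, whose class the sponsor decides under Section 7.2.2. There are two downsides. The follow-up items can no longer be compared with the source wording. Shorter windows 6 months apart also fall in different seasons for each family, which should be noted in reporting. The change helps only families not yet asked at baseline, because a short-window baseline answer cannot be recovered later.

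If the 12-month wording is kept at follow-up, report the two items as descriptions of family circumstances, state the overlap, and do not present them as a measure of change over the intervention.
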